Important medical events that may not result in death, be life-threatening, or require hospitalization may be considered a serious adverse drug experience when, based upon appropriate medical judgment, they may jeopardize the patient or subject and may require medical or surgical intervention to prevent one of the outcomes listed in this definition. Examples of such medical events include allergic bronchospasm requiring intensive treatment in an emergency room or at home, blood dyscrasias or convulsions that do not result in inpatient hospitalization, or the development of drug dependency or drug abuse (21 CFR 312.32).

• Important medical events as defined above, may also be considered serious adverse events. Any important medical event can and should be reported as an SAE if deemed appropriate by the Principal Investigator or the IND Sponsor, IND Office.

• All events occurring during the conduct of a protocol and meeting the definition of a SAE must be reported to the IRB in accordance with the timeframes and procedures outlined in "The University of Texas M. D. Anderson Cancer Center Institutional Review Board Policy for Investigators on Reporting Unanticipated Adverse Events for Drugs and Devices". Unless stated otherwise in the protocol, all SAEs, expected or unexpected, must be reported to the IND Office, regardless of attribution (within 5 working days of knowledge of the event).

• All life-threatening or fatal events, that are unexpected, and related to the study drug, must have a written report submitted within 24 hours (next working day) of knowledge of the event to the Safety Project Manager in the IND Office.

• Unless otherwise noted, the electronic SAE application (eSAE) will be utilized for safety reporting to the IND Office and MDACC IRB.

• Serious adverse events will be captured from the time of the first protocol-specific intervention, until 30 days after the last dose of drug, unless the participant withdraws consent. Serious adverse events must be followed until clinical recovery is complete and laboratory tests have returned to baseline, progression of the event has stabilized, or there has been acceptable resolution of the event.

• Additionally, any serious adverse events that occur after the 30 day time period that are related to the study treatment must be reported to the IND Office. This may include the development of a secondary malignancy.

Reporting to FDA:

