We will summarize patient characteristics of all patients enrolled in the pilot study. Means and standard deviation or medians and IQRs will be calculated. We will also perform exploratory analyses on the changes in FACIT-F subscale (primary outcome measure) from baseline to Day 29 and baseline to Day 57. Similar analysis will be conducted for the secondary outcomes (FACT-G, ESAS symptoms, HADS, SDMT, six- minute walk test, Borg Scale, GSE and Hand Grip Strength and Endurance Test). Based on whether the data is normally distributed (Shapiro-Wilk test) we will use paired t-tests or Wilcoxon Ranked Sum tests. We will also summarize fatigue scores, other secondary outcomes at each point in time and the frequency and type of side effects as determined by NCI CTCAE V4 criteria.

Safety Monitoring

Safety Monitoring

Because this Panax ginseng has not been previously evaluated in cancer related fatigue, we will implement this study in two phases and we will utilize early stopping rules for dose-limiting toxicities (DLTs) for 30 patients in the treatment arm (Arm 2, Panax ginseng 800mg/day) before the main phase of the study begins. A DLT is defined as any Grade 3 or 4 toxicity that is attributable to the treatment regimen.

In the first phase, we will enroll up to 30 evaluable patients in the Arm 2 (treatment arm); patients will not be enrolled in the placebo arm. Recruitment for the main study will be delayed until these original 30 patients are evaluated for DLTs. We will base early stopping rules on a method proposed by Thall et al., (160) and using the Multc99 software from the Department of Biostatistics.

To ensure that the true DLT rate is sufficiently low, we will terminate the study early if the probability that the estimated toxicity rate is greater than 10% (given the results) is greater than 0.95. We assume a prior of Beta (0.1,0.9) in these calculations. The study will be stopped early if (# patients with DLT) / (# patients evaluated) >= 3/6, 4/10, 5/16, 6/22, or 7/29.

The table below shows operating characteristics given differing true toxicity rates based on 10000 simulations for each row:

	Probability	Achieved Sample Size		
True DLT rate	Early Stopping	25 th , 50 th , 75 th percentiles		
1%	<0.0001	30	30	30

Operating Characteristics for first phase early stopping rule (based on DLT)

3%	0.002	30	30	30
5%	0.013	30	30	30
8%	0.053	30	30	30
10%	0.116	30	30	30
15%	0.324	20	30	30
20%	0.597	9	21	30
25%	0.791	8	14	27
30%	0.917	6	9	17
40%	0.993	6	7	9

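### As worded, the Phase I DLT count leaves out attributable Grade 5 events; as a minor point, the first look at six patients is not stated

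*Combined protocol and SAP*

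**What the plan says.** C.9, Safety Monitoring, sets a Bayesian early-stopping rule for the 30 single-arm Phase I patients. The event counted is given as "A DLT is defined as any Grade 3 or 4 toxicity that is attributable to the treatment regimen". The trial stops if "the probability that the estimated toxicity rate is greater than 10% (given the results) is greater than 0.95". On the prior: "We assume a prior of Beta (0.1,0.9) in these calculations". The resulting limits, as patients with a DLT over patients evaluated, are ">= 3/6, 4/10, 5/16, 6/22, or 7/29". A table of operating characteristics follows, "based on 10000 simulations for each row". The next paragraph has the DSMB judge DLT incidence by arm in Phase II, using the same term.

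Deaths appear elsewhere:

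- C.8 on serious adverse events: "All life-threatening or fatal events, that are unexpected, and related to the study drug, must have a written report submitted".
- The C.8 table of recording guidelines has a Grade 5 column.
- C.6, Discontinuation of Study Treatment, lists death as a reason to end treatment.
- C.9, Power Considerations, has each interim analysis compare the arms on adverse events above Grade 2, which takes in Grade 5.

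C.6 and C.9 make a patient evaluable after a single dose.

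**The concern.** Phase I exists to check safety before randomisation, and the DLT count is the only input to its stopping rule. A patient who has taken one dose is in the denominator. If that patient dies of an attributable toxicity and no Grade 3 or 4 event was recorded first, the wording gives no DLT to count. The most severe outcome then lowers the estimated rate. The later DSMB review inherits the definition.

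The criterion and the list also look inconsistent at the start. The criterion carries no minimum number of patients, but the first limit is at six. With two DLTs in the first three patients, the criterion says stop and the list does not.

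**Working it through.** **Inputs (all C.9, Safety Monitoring).** Prior Beta(0.1, 0.9); threshold rate 0.10; cut-off 0.95; up to 30 patients; the five listed limits; the stated stopping probabilities.

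**Step 1: reproduce the boundaries.** With x DLTs in n patients the posterior is Beta(0.1 + x, 0.9 + n − x). The rule stops when 1 − F(0.10) > 0.95, where F is the cumulative distribution function of that posterior. From n = 6 the smallest x that stops is 3 for n = 6–9, 4 for 10–15, 5 for 16–21, 6 for 22–28 and 7 for 29–30. These changes fall exactly at the listed limits.

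**Step 2: reproduce the table.** Exact forward recursion of the binomial path, looking after every patient and removing paths that reach the limit:

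| True DLT rate | Stated P(stop) | Looks from n = 6 | Looks from n = 1 |
|---|---|---|---|
| 5% | 0.013 | 0.013 | 0.023 |
| 10% | 0.116 | 0.112 | 0.135 |
| 15% | 0.324 | 0.332 | 0.357 |
| 20% | 0.597 | 0.592 | 0.610 |
| 30% | 0.917 | 0.919 | 0.923 |
| 40% | 0.993 | 0.993 | 0.993 |

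Looks from n = 6 fit within simulation error. Looks from n = 1 do not: at 10% the simulation standard error is √(0.135 × 0.865 / 10000) = 0.003, and the gap is 0.019. At a 40% rate the stated sample-size percentiles are 6/7/9, which looks from n = 6 reproduce; looks from n = 1 give 3/4/9. So the table describes a rule whose first look is at six patients, and it is right for that rule.

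**Step 3: how omitting Grade 5 acts.** Take six patients, two with an attributable Grade 3 or 4 event and one with an attributable death and nothing counted before it. Read literally, the count is 2/6, posterior 0.904, and the trial continues. With the death counted it is 3/6, posterior 0.987, and the trial stops.

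**Step 4: size.** Let f be the share of attributable Grade 3 or higher events that are fatal with no earlier Grade 3 or 4 event. This is an assumption; the documents give no figure. At a true rate of 20% the counted rate is 0.20 × (1 − f):

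| f | Counted rate | P(stop) |
|---|---|---|
| 0 | 0.200 | 0.59 |
| 1% | 0.198 | 0.58 |
| 2% | 0.196 | 0.57 |
| 10% | 0.180 | 0.49 |
| 20% | 0.160 | 0.38 |

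**Step 5: a single death.** The highest posterior that one DLT can give is at 1/1, 0.929, which is below 0.95.

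**Step 6: results before six patients.** Posteriors are 0.993 at 2/2, 0.979 at 2/3, 0.958 at 2/4, 0.999 at 3/3, 0.997 at 3/4 and 0.993 at 3/5. All exceed 0.95. Two DLTs no longer meet it at n = 5 (0.933). In the Step 2 table, looking from the first patient moves P(stop) by at most 0.025 (0.332 to 0.357, at 15%).

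**The case against.** The wording is probably a slip for Grade 3 or higher. The Phase II comparison of events above Grade 2 suggests that nobody meant to leave deaths out, and in practice staff would very likely count one. Serious events go to the IND Office whatever their attribution, and unexpected, related fatal events must be reported in writing within 24 hours, so a death would not go unseen. A patient who passes through Grade 3 or 4 before dying is already counted. B.7 describes ginseng's adverse effects as mild and reversible. At a 20% rate, f of 10 to 20% implies 30 × 0.20 × 0.10 = 0.6 to 30 × 0.20 × 0.20 = 1.2 attributable deaths in Phase I.

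Most of this stands, and it limits the size of the point. It does not remove the gap, because neither the reporting route nor the end of one patient's treatment is written as an input to the stopping count.

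On the early looks, a six-patient minimum is a reasonable choice and the table shows that it was the rule evaluated. What remains is that the text does not say so.

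A reader might go further and infer that the boundaries are wrong or that the operating characteristics do not apply. The documents do not support that: the list is exact from six patients and the table reproduces. The table is indexed by true DLT rate, so widening the definition changes what that rate measures and alters no row.

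**Conclusion.** The DLT definition, the Grade 5 column in C.8 and the above-Grade-2 comparison in C.9 need to be reconciled. Taken literally, the Phase I count treats an attributable death with no earlier Grade 3 or 4 event as no DLT. The loss in stopping probability at a true 20% rate runs from about 0.01 to 0.02 (f of 1 to 2%) to 0.10 (f of 10%) and 0.21 (f of 20%). The larger losses rest on fatal shares that the documents do not support and should not be read as expected effects. Nor should a reader infer that counting one death would stop the trial, since it would not.

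The early-look mismatch is minor. It is confined to the first five patients, changes overall stopping probability by about 0.025 or less, and comes from a minimum that was applied but not written down.

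**What to change.** 1. Word the DLT definition so that the stopping count covers attributable toxicity of Grade 3, 4 or 5. The DSMB paragraph uses the same term and follows automatically. The cost is one phrase; boundaries, table and sample size do not change.
2. Add one clause stating that the rule is first applied at six evaluated patients. The criterion, list and table then agree, and nothing needs recalculating.

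Adding limits before six patients instead is possible but not needed. It would raise the chance of stopping at a 5% DLT rate from 0.013 to 0.023, and only then would the table have to be re-issued.

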Patients will be randomly assigned to one of the two treatment arms. The randomization schema will be based on parameters input into RANLST, a randomization program developed at UTMD Anderson and supported by an NCI grant.

C.6. Clinical Trial Design and Treatment Plan:

This study will have (1) Phase I: an initial non dose escalating phase to evaluate dose limiting toxicity. A total 30 evaluable patients will be enrolled in this phase. After study completion of the 30 evaluable patients (2) Phase II a second phase- RCT double blind phase will be started and (3) Both phases will have an open labeled phase. Patients in both Phase I or II may continue the ginseng in the open labeled extension phase if there are no grade 2 or more toxicity as per CTRC criteria as determined by the PI. A

total of 158 eligible patients will be enrolled in both phases of the trial (30 evaluable in phase I + 128 in phase II). (See Study Design Fig. 6).

Evaluable patients will be defined as any patient enrolled on the study that has taken at least one dose of treatment (i.e., either ginseng or placebo), making them available for toxicity and response.

C.6.1. Double-Blind Phase Dosing Patients will be randomized to one of two experimental groups receiving the treatments detailed below.

- The placebo group (**Arm 1**), will receive oral placebo twice daily for 29 days.
- The Panax ginseng group (Arm 2) will receive ginseng capsules 400 mg twice daily for 29 days.

Unblinding Procedure:

- 1. The Statistician and the investigational pharmacist will have access to the codes/assignments.
- 2. The codes will be revealed only If there is a safety issue and the treating physician needs to be aware of the treatment assignment.
- 3. The PI should be contacted regarding and give approval for un-blinding
- 4. The Investigator/research team must inform the IND Office when un-blinding occurs.

C.6.2. Open-Label extension Phase

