This is a preliminary study to explore the efficacy of P. ginseng in reducing fatigue as measured by the Functional Assessment of Cancer Therapy- Fatigue (FACIT-F) subscale. Because this Panax ginseng has not been previously evaluated in cancer related fatigue, we will implement this study in two phases. In the first phase(initial non dose escalating phase), we will enroll up to 30 patients in the Arm 2 (treatment arm); patients will not be enrolled in the placebo arm. Recruitment will be halted until these original 30 patients can be evaluated for DLTs. In the second, main phase patients will be randomized to receive either Panax ginseng or placebo. As a

2009-0854 January 21, 2016 Page 23 of 33

primary analysis, we will assess the level of fatigue at baseline and after 29 days to determine group differences in fatigue changes over time using analysis of variance. This analysis will test for differences between groups, differences over time, and a group by time interaction. We will also perform a repeated measures analysis by group using all available time points (for the FACIT-F fatigue subscale at baseline, day 15 and day 29). This analysis will test for differences between groups, differences over time, a group by time interaction, and trends over time. For all analyses of continuous variables, if the data are not approximately normally distributed, we will either use a nonparametric equivalent of the statistical test or we will transform the variable to achieve approximate normality. The design of the study is intent to treat, i.e., it is our aim to analyze anyone who received at least a single dose for both toxicity and response. Response would be considered clinical beneficial if they improve 3.5 points on the FACIT- F fatigue subscale at day 29 or day 15 (if day 29 is unavailable). Patient who have not completed at least day 15 would be considered inevaluable for consideration of clinical benefit.

Pilot Analysis:

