During the second phase of the study, the DSMB will meet to assess toxicity in an unblinded fashion at defined intervals (annual review) and will terminate the study if the incidence of DLT on either arm is judged by the DSMB to be excessive.

Power Considerations: There are no randomized controlled trials on P.ginseng for the management of CRF. The only intervention with Level I evidence for effectiveness in CRF is exercise. Among the most important clinical trials conducted on the intervention are those of Segal etal [154-156]. They have determined the clinically important difference in fatigue as a result of intervention as compared to placebo. Since these two studies used FACIT-F (our primary outcome) we have used these studies for power/sample size calculation. We postulate that if P.ginseng is an effective intervention we will observe a difference in response at Day 29(primary end point) similar and higher to those observed in the Exercise studies. We plan to include 50 evaluable patients per group. If we assume that our dropout rate will be no higher than 20%, we will recruit 64 patients into each group, for a total of 128 patients. As we could find no other published studies about the use of Panax ginseng in cancer patients, we base our sample size estimate on previous research in resistance exercise training [154]. This study found that the difference between groups in changes in the FACIT F subscale at 24 weeks was 4.78, significant at p=0.002, and was powered to detect a difference of 3.5 points based on a similar study in exercise resistance [155] that found standard deviations in difference scores over 12 weeks of 5.8. Studies such as Cella et al, 2002[156], state that differences of 3-5 points or more on the FACIT-F subscale are clinically important differences. If we assume a standard deviation of 5.8 in difference scores, with 50 evaluable patients per group we will be able to detect differences as small as 3.3 or larger with a twosided significance level of 0.05 and 80% power. With standard deviations in difference scores as large as 8.8, we will still be able to detect differences of 5 points or greater.

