Evaluable patients will be defined as any patient enrolled on the study that has taken at least one dose of treatment (i.e., either ginseng or placebo), making them available for toxicity and response. Although we expect dropouts (20% of 128 patients) the primary analysis will not include dropouts, but a secondary analysis would carry forward the last known FACIT-F score for those patients who had received at least one dose.

Yearly interim analyses will be conducted by the biostatistician and the results will be presented to the MDACC DSMB office. Results will be presented overall and by arm retaining the blinding as to arm assignment unless requested to reveal arm assignment by the DSMB (usually only made if one or both of the arms show a significantly less than expected efficacy or toxicity). In that case the statistician will reveal the arm assignments to the DSMB. The PI and other collaborators (other than the statistical collaborator) will remain blinded as to the arm assignments of patients.

As a part of each interim analysis, we will determine if either arm has significantly more occurrences of greater than grade 2 adverse events (p<0.05) as compared to each other. If this is found it will be reported to the DSMB and the study may be terminated early.

A formal interim analysis will be conducted when a total of 50 evaluable patients (one-half of the total number of evaluable patients) have been evaluated for 29 days. This interim analysis will allow for the early termination of the study in light of evidence that patients in either arm improve significantly than the other arm (early stopping due to superiority) or that patients in the two arms have similar improvement (early stopping due to futility). In order to provide for an overall two-sided significance level of approximately 0.05 for the study, the interim analysis will have a Lan-DeMets monitoring boundary with an O'Brien-Fleming stopping rule for both tests (EaSt, version 5, Cytel Software Corporation). The decision boundaries for the interim test will be to accept the null hypothesis of no treatment difference (futility) if the test statistic |Z| < 0.348 (p > 0.73), reject the null hypothesis if |Z| > 2.96 (p < 0.003), or otherwise continue the trial. The final test cut-off will be to reject the null hypothesis if |Z| > 1.95 (p < 0.051).

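### The primary fatigue analysis leaves out dropouts, which contradicts the plan's own intent-to-treat, one-dose rule

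*Combined protocol and SAP*

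**What the plan says.** Section C.9 states the principle: "The design of the study is intent to treat, i.e., it is our aim to analyze anyone who received at least a single dose". It applies this to response as well as to toxicity. Section C.6 and the text after Power Considerations define evaluable in the same way: "Evaluable patients will be defined as any patient enrolled on the study that has taken at least one dose of treatment".

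The primary analysis in C.9 compares FACIT-F change from baseline to Day 29 between arms. The sentence after the second one-dose definition expects dropouts at 20% of 128 and then says "the primary analysis will not include dropouts, but a secondary analysis would carry forward the last known FACIT-F score", limited to patients who had at least one dose. The excluded group can therefore include dosed patients.

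Two other rules bear on missing data. C.9 adds "We will also perform a repeated measures analysis by group using all available time points", meaning baseline, Day 15 and Day 29, but as an addition to the primary analysis. For clinical benefit only, Day 15 may stand in for Day 29, and "Patient who have not completed at least day 15 would be considered inevaluable for consideration of clinical benefit".

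Power Considerations says "We plan to include 50 evaluable patients per group", from 64 recruited per group. The interim analysis is triggered when "a total of 50 evaluable patients (one-half of the total number of evaluable patients) have been evaluated for 29 days".

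**The concern.** The final test and the interim superiority and futility rules rest on the Day-29 comparison, so the patients who enter it must be fixed by one rule. Two statisticians could follow this text in good faith and build different primary populations: one of all dosed patients, the other of completers only.

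The word *dropout* is never defined. The natural reading is a patient with no Day-29 FACIT-F score. However, the dose-modification table lets patients be taken off study drug and monitored, and the notes to Table 3 allow FACIT-F by telephone when a patient cannot attend. A patient could stop drug early and still have a Day-29 score. The plan does not say whether that score counts.

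Excluding patients after randomisation can also bias the comparison if dropout is related to fatigue and differs between arms. The sample-size allowance for dropout protects power but not the comparability of the arms.

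**Working it through.** **1. The plan's own figures.** Inputs from Power Considerations: SD of change 5.8, difference 3.3, two-sided alpha 0.05, 50 per arm.
- Power = Φ(3.3 / (5.8 × √(2/50)) − 1.96) = 81%, so the stated 80% reproduces.
- Recruitment: 50 / 0.80 = 62.5, so 63 per arm against 64 stated.
- Exclusion: 0.20 × 128 = 25.6, about 26 patients. Left per arm: 64 × 0.80 = 51.2.

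The sample size is sound. It uses evaluable to mean patients who did not drop out, which is not the one-dose definition.

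**2. The interim count.** Half of a one-dose total would be 64 of 128. Fifty is half of 100, and the trigger requires 29 days of evaluation. The Lan-DeMets O'Brien-Fleming boundary at information fraction 0.50 is 2.96, as printed. The boundary is correct for 50 of 100, so this is a matter of wording.

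**3. Bias of the completer analysis with no true effect.** These assumptions are not in the documents: SD of change 5.8 at both visits; Day-15/Day-29 correlation 0.7; mean change 2 at Day 15 and 3 at Day 29 in both arms; dropout after Day 15, logistic in Day-15 change, odds ratio 2.5 per SD worse.

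In each arm, completer mean − all-patient mean = dropout rate × (completer mean − dropout mean). The gap under these assumptions is about 3.3 points.

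| Dropout, placebo / ginseng | Completer bias | Completer type I error |
|---|---|---|
| 20% / 20% | 0 | 5% |
| 18% / 22% | +0.12 | 5.1% |
| 15% / 25% | +0.31 | 5.9% |

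For the last row, (0.25 − 0.15) × 3.3 = 0.33 approximately; integration gives 0.31. For the error rate, 64 × 0.85 = 54.4 and 64 × 0.75 = 48 remain, SE = 5.8 × √(1/54.4 + 1/48) = 1.15, and 0.31 / 1.15 = 0.27. Then Φ(−1.96 + 0.27) + Φ(−1.96 − 0.27) is about 5.8%; simulation gives 5.9%. Over odds ratios of 1.5 to 4 and correlations of 0.5 to 0.8, bias at 15% / 25% runs from +0.11 to +0.45.

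Equal rates alone are not enough. If the gap were 3.5 to 5 points in one arm and zero in the other, 20% dropout in both arms would give 0.20 × 3.5 = 0.7 to 0.20 × 5 = 1.0 point.

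**4. LOCF in the same 15% / 25% case.** In each arm, LOCF error = dropout rate × (dropouts' Day-15 mean − dropouts' Day-29 mean). The bias between arms is therefore a fixed part of −0.08 plus 0.10 × (Day-15 mean change − Day-29 mean change).

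| Mean change, Day 15 then Day 29 | LOCF bias | Completer bias |
|---|---|---|
| 2 then 3 | −0.18 | +0.31 |
| 3 then 3 | −0.08 | +0.31 |
| 3 then 2 | +0.02 | +0.31 |
| 4 then 2 | +0.12 | +0.31 |

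The documents give no trajectory, so the sign is unknown. With a true effect of 3.3, half of it present by Day 15, and 20% dropout in both arms, LOCF gives 0.8 × 3.3 + 0.2 × 1.65 = 2.97.

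**5. What a likelihood model using Day 15 offers.** In the cases in step 3's table its bias is zero, because dropout there depends only on the observed Day-15 change. If half of dropout occurs before Day 15 (15% / 25%), it keeps +0.12 against +0.31 for completers. For precision when dropout is unrelated to fatigue, effective n per arm = 1 / [(1 − r²)/51.2 + r²/64], which is 53.9, 56.8 and 58.7 for r = 0.5, 0.7 and 0.8. The detectable difference, 2.80 × 5.8 × √(2/n), falls from 3.21 at n = 51.2 to 3.13, 3.05 and 3.00.

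**The case against.** The strongest reply concerns size. At the only dropout rate in the documents, 20% with no split by arm, the completer analysis is unbiased when the completer-dropout gaps are equal. A 10-point difference between arms must be assumed to reach 0.3 points. The trial calls itself preliminary and is meant to inform a larger one. This stands, and it limits the point to a should-fix.

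The plan also already has a repeated-measures analysis over all time points and a carried-forward analysis of dosed patients. That stands too: the remedy is mostly a re-ranking. It does not remove the conflict, because neither analysis is primary and the repeated-measures model is not stated to be likelihood-based.

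One could say that the intent-to-treat sentence concerns only the 3.5-point responder measure. That does not help, since the same paragraph makes dosed patients without Day 15 inevaluable for that measure.

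Three stronger readings are tempting. A reader might infer that the primary result will be biased, but nothing in the documents shows that dropout will differ by arm. A reader might infer that LOCF always errs in the opposite direction to the completer analysis; step 4 shows that this depends on an unknown trajectory. A reader might infer that the one-dose definition makes the interim boundary wrong; step 2 shows that it does not.

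**Conclusion.** The plan is wrong as written and should be fixed. It states an intent-to-treat, one-dose principle and then sets a primary analysis that drops about 26 of 128 patients, including dosed ones. The conflict rests on the text alone and needs no assumption. The 26 is a planning figure, since Power Considerations treats 20% as an upper limit. The one-dose set is itself a modified intent-to-treat set; the point holds the plan only to its own rule.

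The bias figures are illustrative: zero with equal dropout and equal gaps, and about 0.3 of the 3.3-point detectable difference at an assumed 15% against 25%. LOCF bias ran from about −0.18 to +0.12 in the cases checked, so LOCF is not a dependable check on the primary result.

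**What to change.** - Reconcile the two statements in C.9. Make the planned repeated-measures analysis primary: a likelihood-based model of baseline, Day 15 and Day 29 with arm by visit, in all randomised patients who took at least one dose, testing the arm difference in change at Day 29.
- Define dropout as having no Day-29 FACIT-F score. Include every score collected after study drug is stopped, and state that the telephone route in the notes to Table 3 covers those patients.
- Keep the completer and LOCF analyses as supportive.
- Use *Day-29 FACIT-F available* for the 50 per arm and the interim trigger of 50. Reserve *evaluable* for the one-dose definition.
- If the model is used at the interim, compute the information fraction from it. Patients with only a Day-15 score add information, so the fraction need not be 0.50. If it is not, recalculate the 2.96, 0.348 and 1.95 boundaries.

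The cost is wording, some programming and the interim check. No patients or visits are added, since Day-15 and Day-29 FACIT-F are already in Table 3; telephone contact after stopping drug is extra only if it is not already done. The model assumes data are missing at random and helps little for patients lost before Day 15. A delta-adjusted sensitivity analysis for that group is optional.
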